CRO: Clinical Research Organization	PTT: Partial thromboplastin time
CPK: creatine phosphokinase	PUO: Partial Urethral Obstruction
E-CRF: electronic case report form	QoL: Quality of Life
CRP: C- reactive protein	QTcF: QTc Fridericia / QTcB: QTc Bazett
CSR: clinical study report	RBC: red blood cell
DBP: diastolic blood pressure	SAE: serious adverse event
DO or DH: Detrusor overactivity	SAP: statistical analysis plan
dL: deciliters	SBP: systolic blood pressure
DLT: Dose limiting toxicity	SD: standard deviation
DRF: discrepancy resolution form	SF-12: Health Status Questionnaire

List of Abbreviations

DSMB: Data Safety Monitoring Board	SGOT: serum glutamic-oxaloacetic transaminase
ECG: electrocardiogram	SGPT: serum glutamic-pyruvic transaminase
FDA: Food and Drug Administration	TEAE: treatment-emergent adverse event
FSH: Follicular stimulating hormone	ULN: upper limit of normal
g: gram	NOBLE: N ational O veractive B ladder E valuation
GCP: good clinical practices	UUI: urge urinary incontinence
GeMCRIS: Genetic Modification Clinical Research Information System, NIH	
GGT: gamma glutamyltransferase	
KHQ: King's Health Questionnaire	
K ⁺ : potassium	
LDH: lactate dehydrogenase	
LLN: lower limit of normal	
h: hour	
HR: heart rate	
hpf: high powered field	
ICH: International Conference on Harmonization	
ICIQ-SF: International Consultation on Incontinence Questionnaire- Short Form)	
IEC: independent ethics committee	
IRB: institutional review board	
ITT: intent-to-treat	
kg: kilogram	
L: liter	

Protocol Synopsis

Title A Phase 1 Multicenter Study Evaluating the Safety and Potential Activity Of Two Escalating Doses of *hMaxi-K* Gene Transfer By Direct Injection into the Bladder Wall In Female Participants With Idiopathic (Non-neurogenic) Overactive Bladder Syndrome and Detrusor Overactivity: Double Blind, Imbalanced Placebo Controlled Design Within 2 Sequential Active Treatment Groups

Study No. ION 03-OAB

Study Phase Phase 1

No. of Sites Up to six clinical sites in USA

Study Objectives The primary objective of this study is to evaluate occurrence of Adverse Events and their relationship to *hMaxi-K* following multiple intramuscular (IM) injections into the bladder wall. Two dose levels (16000 µg and 24000 µg by IM injection into the bladder wall) in females with moderate OAB/DO of \geq six months duration are initially planned. **Pending safety and efficacy results for the 2 doses that are planned, the protocol may be amended to investigate additional doses in this study.**

The secondary objectives of this study are to evaluate the following safety parameters:

- Clinical laboratory tests- changes from baseline
- Electrocardiogram change from baseline
- Physical Examination- changes from baseline

These changes will be evaluated primarily at the individual level, through clinical assessment of outliers supported by descriptive statistics. In addition efficacy parameters will be evaluated (change from baseline compared to placebo), including number of micturitions per day, volume per micturition, incontinence episodes, pad weight, uninhibited contractions during cystoscopy, and general and bladder specific quality of life assessments.

Study Design This study is a double blind, placebo-controlled, multicenter, sequential active dose, phase 1 study in females with moderate OAB/DO of \geq six months duration. The proposed study period is approximately 6 months following a single administration of study drug by multiple IM injections into the bladder wall per participant. The protocol sample size of this phase I study is not intended to support the statistical significance of the primary endpoint as outlined in the study objectives. Rather, the sample size takes into account clinical safety considerations. Nine participants per dose level are planned: [6 assigned active treatment and 3 assigned placebo (PBS-20% sucrose only control group)]. Therefore a total of up to 9 participants will be enrolled in each dose group. Each arm of participants will be enrolled sequentially and enrollment into the next higher dose level will be dependent on assessment of safety. The participants chosen will be assigned in a

**Study
Population**

randomized fashion to either placebo or an active treatment group within each group.

The study population is women ≥ 18 years old of non-child bearing potential¹ with overactive bladder (OAB) and detrusor overactivity who are otherwise in good health.

The target population is women with idiopathic (non-neurogenic) OAB and detrusor overactivity (DO) who have been unable to tolerate, do not wish to continue, or have had unsuccessful results with, prior therapy for OAB/DO. OAB is characterized by a decreased bladder capacity, frequent voiding, frequent sensations of a strong urge to void, and in some patients, episodes of incontinence. DO is one or more uncontrolled phasic contraction(s) of the detrusor of at least 5 cm/H₂O pressure that are observed during urodynamic testing with or without urinary leakage.

Inclusion criteria will include clinical symptoms of overactive bladder of ≥ 6 months duration including at least one of the following:

- a. Frequent micturition ($\geq 8/24$ hrs)
- b. Symptoms of urinary urgency (the complaint of sudden compelling desire to pass urine, which is difficult to defer) or nocturia (the complaint of *waking* at night two or more times to void)
- c. Urge urinary incontinence (average of 5 per week – Urge urinary incontinence is defined as: the complaint of involuntary leakage accompanied by or immediately preceded by urgency)

Participants must also have a bladder scan at screening demonstrating a residual volume of ≤ 200 ml and detrusor overactivity documented during baseline urodynamic testing of ≥ 1 uncontrolled contraction(s) of the detrusor of at least 5 cm/ H₂O.

¹ All female participants must be of non-childbearing potential (e.g., hysterectomy, tubal ligation or post menopausal defined as last menstrual cycle >12 months prior to study enrollment, or serum FSH >40 mIU/L).

Study Procedures There will be a total of 9 visits (V) and a 1 and 3 day post dosing telephone contact with the patient to evaluate for any new complaints. Following screening (V1, V1A) and study drug administration at week 0 (V2), eligible participants will be evaluated for safety post dosing with study drug at weeks 1 (V3), 2 (V4), 4 (V5), 8 (V6), 12 (V7), and 24 (V8).

At Screening (V1), Baseline (prior to dosing) and 1 (V3), 2 (V4), 4 (V5), 8 (V6), 12 (V7) and 24 (V8) weeks post dosing participants will have a complete physical exam including urogenital examination. (ECG) will be performed at Screening (V1), at Baseline (V2 prior to dosing and at 2 hours post dosing), at one week post dosing (V3), 4 weeks post dosing (V5), and at the final visit (V8).

Laboratory evaluations including chemistry, hematology, and urinalysis will be performed at Screening (Week -2 (V1), Baseline (prior to dosing; V2) and Weeks 1 (V3), 2(V4), 4 (V5), 12 (V7) and 24 (V8) weeks post dosing. At Baseline (V2) no chemistries required. At V1A and prior to dosing at V2, urinalysis will be done by Dipstick. No chemistry or hematology required at V1A. No chemistry, hematology, urinalysis or urine culture required at V6. Urine cultures will be done at V1 (by catheterization with a urodynamic catheter), at V3 (clean void), at V1A, V2, V5 and V8 prior to cystometry or cystoscopy (by catheterization with the urodynamic catheter) and before discharge by clean void to insure the absence of infection (at V2 it will be the first clean voided urine after study drug dosing).

At Screening (V1) and at 2 (V4), 8 (V6), and 24 (V8) weeks post dosing participants will have a bladder scan to evaluate for residual volume. Participants will be assessed for study drug effects on incontinence at Screening (V1A), and at Week 4 (V5) and Week 24 (V8) by cystometry. Participants will complete a daily diary at home for 7 days prior to the baseline (prior to V2). Prior to V1A they should complete diaries as well which may be less than 7 days, but can be used to evaluate for compliance and inclusion criteria such as incontinence. Diaries will capture number of micturitions, volume of micturitions, number of urge incontinence episodes, and rating of episode, and the number of pads used every 72 hours. The participants will continue to complete this daily diary during the course of the trial and the diary will be evaluated at each follow-up visit. Diaries will be assessed at 1, 2, 4, 8, 12, and 24 weeks after treatment. Micturition diaries will be completed **daily for 7 days prior to treatment and 7 days prior to each visit after treatment. Pads will be collected for up to 72 hours prior to V1A, prior to V2 and prior to all visits thereafter.**

The participants' perception of their bladder condition will be rated at Baseline (prior to dosing) and at weeks 1, 2, 4, 8, 12, and 24 post dosing and their opinion of response to treatment assessed after 1, 2, 4, 8, 12, and 24 weeks following the study drug administration. QoL will be assessed with the Kings Health Questionnaire (KHQ) and SF-12 at Baseline (prior to dosing) and thereafter at weeks 4, 8, 12, and 24 weeks post dosing.¹

All participants will be administered the International Consultation on

Incontinence Questionnaire – Short Form (ICIQ-SF) at Baseline and at 4, 8, 12, and 24 weeks following administration of study drug.

In all participants, **urine and blood specimens** will be collected to assay for the presence of *hSlo* DNA by PCR. If they are positive, for the *hSlo* after 6 months, urine and/or blood specimens will be collected monthly thereafter (post study) until 2 consecutive specimens are negative. On the day of dosing, blood and urine will be collected pre-dosing and 2 hours post-dosing.

Primary Outcome	Safety will be assessed by analysis of adverse experiences, clinical laboratory tests, electrocardiogram, and physical examinations.
Secondary Outcomes	
The mean number of micturitions per 24 hours will be evaluated at all visits and changes compared to baseline and placebo.
 
The mean volume per micturition will be evaluated at all visits and changes compared to baseline and placebo.
 
The change in the mean number of urge incontinence episodes per 7 day collection period and the urgency episodes per 24 hours will be evaluated at all visits and compared to baseline and placebo.
 
The change in detrusor overactivity at week 4 and 24 will be evaluated and compared to baseline and placebo.
 
Urgency will be rated with a 4 point validated urgency scale included in the voiding diary.
 
Participants will rate their perceived bladder condition severity using a validated 6-point scale and assess their response to treatment. Improvement will be defined as a decrease of 1 point or more from baseline. Participants' assessment of Quality of Life (QoL) will be evaluated using the Kings Health Questionnaire algorithm and changes compared to baseline and placebo.
 
Changes from baseline at the final visit (24 weeks) in bladder capacity will be evaluated and compared to baseline and placebo.

Study Duration	6 months (24 weeks) per participant with an additional 18 month safety follow-up.
Study Start	November, 2013
Sample Size	Maximum of 18 participants.
Statistical Analysis	Both the safety data and data to assess activity will be analyzed using summary descriptive statistics for the four cohorts and the total study population. The group sample sizes of 6 per arm achieve 80% power to detect a 30% reduction in frequency of voiding to placebo assuming a standard deviation of 2.5 with a significance level of 0.05 using a two-sided, two sample t-test. A comparison to baseline will also be done using a two-sided t- test. Total number of active treatment participants (N=12) will also be compared to total number of placebo participants (N=6).

Table 1. Procedures By Visit

Phase	Screening Phase			Post-Treatment Follow up Visits						
	Visit 1	Visit 1A ⁿ	Visit 2	Telephone Follow-up ^j	Visit 3	Visit 4	Visit 5	Visit 6	Visit 7	Visit 8
Day	-14	-14 to -8	0 (Baseline)	Day 1 & 3	8	15	29	57	85	169 (Final)
Week	-2		0	0	1	2	4	8	12	24
Visit Window (days)		+2	+2	Day 3±1	+2	+2	±2	±3	±5	±5
Signed Informed Consent	▲									
Evaluation of Inclusion /Exclusion Criteria	▲	▲	▲ ^f							
Demographics and Medical/ Surgical History	▲									
Physical Examination	▲		▲ ^f		▲	▲	▲	▲	▲	▲
ECG	▲		▲ ^a		▲		▲			▲
Previous / Concomitant Medication Assessment	▲	▲	▲ ^f		▲	▲	▲	▲	▲	▲
Vital Signs ^b	▲		▲ ^{f,l}		▲	▲	▲	▲	▲	▲
Objective OAB /DO Evaluation (Cystometry) ^b		▲ ^d					▲			▲
Bladder scan ^c	▲					▲		▲		▲
Dispense Daily Voiding Diary/Urgency questionnaire ⁱ	▲	▲	▲ ^f		▲	▲	▲	▲	▲	
Pad Test ^m		▲	▲		▲	▲	▲	▲	▲	▲
QoL (King’s Health Questionnaire) and SF-12			▲ ^f				▲	▲	▲	▲
Subjective Evaluation of Disease State ^k			▲ ^f		▲	▲	▲	▲	▲	▲
Subjective Evaluation of Response to Treatment ^k					▲	▲	▲	▲	▲	▲
ICIQ-SF			▲ ^f				▲	▲	▲	▲
Urinalysis and Urine Cultures ^d	▲	▲	▲ ^f		▲	▲	▲		▲	▲
Hematology Laboratory Tests ^e	▲		▲		▲	▲	▲		▲	▲
Chemistry Laboratory Tests ^e	▲				▲	▲	▲		▲	▲
Pharmacokinetic Assessment (urine and blood hSlo cDNA)			▲ ^{f,g}		▲	▲	▲	▲	▲	▲ ^g
Adverse Event Assessment		▲	▲ ^f	▲ ^j	▲	▲	▲	▲	▲	▲
Study Drug administered			▲							

- a. ECG will be done prior to administration of study drug and at 2 hours post dosing.
- b. Cystometry includes: volume at first desire to void, detrusor pressure, abdominal pressure, detrusor pressure at beginning of voiding, detrusor pressure at maximum flow, maximum detrusor pressure, volume at strong urge to void, peak flow rate during voiding, voided volume, volume at DO, post-void residual volume, total bladder volume (voided volume + residual volume), number of detrusor contractions during procedure and duration of DO
- c. Inclusion criteria specify residual volume ≤200 ml. Bladder scans at V1 and V8 to be done before catheterization.
- d. Urinalysis with microscopic RBC and WBC, protein, glucose, nitrites, pH, and specific gravity at V 1, 3-5 and V7 and V8. At V1A and V2, urinalysis by Dipstick will be done. Urine cultures at V1 (by catheterization with the urodynamic catheter), V3 (clean void); at V1A, V2, V5 and V8 prior to cystometry or cystoscopy (by catheterization with the urodynamic catheter) and before discharge by clean void (at V2 use first voided urine after drug administration). Visit 2 urinalysis by Dipstick will be done prior to dosing and urine culture will be performed both prior to study drug administration and prior to discharge
- e. Lab tests to be done at V1, V2 - 5, V7 and V8 include: Hematology- CBC with differential, platelet count, sedimentation rate, PTT, PT (no PT and PTT at V2 and V4), CRP, Antinuclear antibody; Fasting chemistry- BUN, creatinine, Na⁺, K⁺, Mg⁺⁺, Ca⁺⁺, CO2, Cl⁻, albumin, alkaline phosphatase, ALT, AST, GGT, total bilirubin, total protein, CPK, LDH, glucose; Serum Pregnancy Test for beta-HCG required for women of child bearing age who have not had hysterectomy at Screening V1 and on as need basis. In addition, FSH> 40 IU/L if last menstrual cycle not > 12 months prior to study enrollment. HbA1c will be done at screening Visit 1 only. No chemistries will be done at 2 (Week 0). At V4, chemistries will include only BUN, creatinine, electrolytes (Na⁺, K⁺), CRP, glucose, and ANA. No lab tests will be done at Visit 1A or V6. Lab tests should be taken at the same time of day at all study visits.
- f. Test or procedure will be done prior to administration of study drug at Visit 2. At V2 there is also a urine culture after dosing.
- g. At V2, blood and urine pre-dosing and at 2 hour post-dosing. If specimen is still positive at week 24, participant must return monthly until two successive specimens are negative for *hSlo* DNA.
- h. Vital signs will include height at V1 only; weight at V1 and V8; oral body temperature at all visits (except V1A). Same arm should be used for all BP measurements and specified.
- i. Diaries are to be completed prior to V1A (to test for compliance and inclusion criteria), for 7 days prior to Visit 2 and 7 days prior to each visit, thereafter.
- j. Participants will be contacted by telephone on Study Day 1 and 3 (1 day and 3 days ±1, following drug administration at Visit 2) for assessment of adverse events.
- k. Subjective assessments are based on the following questions in Appendix C: “How bothersome do you consider your bladder problem?” and “Has the treatment been of benefit to you?”
- l. BP will be taken every 15 minutes for 2 hour post administration of study drug.
- m. Participants will bring in pads/diapers worn for 3 days prior to Visit 1A & 2 (if V1A after screening V1) and 3 days prior to all subsequent visits (Visit 3 to Visit 8); also bring in clean pad/diapers to use as baseline.
- n. Visit 1A may occur on same day as V1. In this case all V1A procedures not already to be done at V1 should be completed. Cystoscopy should be performed after all other V1 procedures and post cystoscopy urine culture obtained using clean void. If V1A coincides with V1, then since pad collection and diaries will not be completed prior to V1, these must be checked for compliance at V2.

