3.1 Study Design

This study is a double blind, placebo-controlled, multicenter, sequential active dose, phase 1 study in females with moderate OAB/DO of \geq six months duration.

The proposed study period is approximately 6 months following a single administration of study drug per participant. The protocol sample size of this phase I trial is not intended to find statistically significant differences between placebo and treatment for the primary endpoint as outlined in 2.0. Rather, the sample size takes into account clinical safety considerations. However, the study is designed to observe a 30% reduction in the number of voids following gene transfer using the following calculations with NCSS/PASS program (NCSS, Kaysville, Utah, 84037).

Power ^{29,30, 31}	N1	N2	Ratio	Alpha	Beta	Mean1	Mean2	S1	S2
0.80251	9	10	1.111	0.05000	0.19749	10.0	6.6	2.5	2.5

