10.3 Efficacy

The sample size has been estimated assuming a standard deviation of 2.5 and a two sample t-test to have 80% power.

The protocol is designed to observe a 30% reduction in the number of voids compared to placebo following gene transfer using the following calculations with NCSS/PASS program (NCSS, Kaysville, Utah, 84037-3233).

Table 10;. Powering									
Power	N1	N2	Ratio	Alph	Beta	Mean	Mean2	S1	S2
0.80251	9	10	1.111	0.050	0.19749	10.0	6.6	2.5	2.5

The mean number of micturations per 24 hours will be evaluated at all visits and changes compared to baseline and placebo.

The other secondary outcome measures will be the change in the mean number of urge incontinence episodes per 24 hours; urgency episodes per 24 hours; mean volume voided per micturition, diminished urgency perception; change in weight of 72 hour pad test; and change in

detrusor overactivity (DO) including peak amplitude, volume at which DO appears and presence or absence of DO. The participants' perception of their bladder condition and response to treatment will be assessed at baseline (Week 0) and after 1, 2, 4, 8, 12, and 24 weeks. Improvement will be defined as a decrease of 1 point or more from baseline. Quality of Life (QoL) will be evaluated using the Kings Health Questionnaire (see Appendix B for algorithm). Change in maximum bladder capacity (difference of pre-treatment to post-treatment volume) as determined by cystometry of *hMaxi-K* versus pool of placebo participants from each treatment level.

Participants will be assessed for changes from baseline in urinary symptoms following administration of *hMaxi-K* using the questions of the ICIQ-SF form and the urgency rating scale. Participants will also be pooled across treatment groups (all active vs. all placebo).

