5. SAMPLE SIZE DETERMINATION

The proposed study period is approximately 6 months following a single administration of study drug per participant. The protocol sample size of this Phase 1 trial is not intended to find statistically significant differences between placebo and treatment for the primary endpoint as outlined in 2. Rather, the sample size takes into account clinical safety considerations.

However, the study is designed to observe a 30% reduction in the number of voids following gene transfer using the following calculations with NCSS/PASS program (NCSS, Kaysville, Utah, 84037).

Power	N1	N2	Ratio	Alpha	Beta	Mean1	Mean2	S1	S2
0.80251	9	10	1.111	0.05000	0.19749	10.0	6.6	2.5	2.5

Nine participants per dose level are planned: [6 assigned active treatments and 3 assigned placebo (PBS-20% sucrose only control group)]. Therefore a total of up to 9 participants will be enrolled in each dose group. Each arm of participants will be enrolled sequentially and enrollment into the next higher dose level will be dependent on assessment of safety. The participants chosen will be assigned in a randomized fashion to either placebo or an active treatment group within each group.

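### The claimed 80% power with 6 per arm for a 30% reduction in voids is wrong: the planned comparisons have about 47% (6 vs 6) and 62% (12 vs 6)

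*Protocol*

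**What the plan says.** The Statistical Analysis entry of the protocol synopsis states: "The group sample sizes of 6 per arm achieve 80% power to detect a 30% reduction in frequency of voiding to placebo". The inputs named there are SD 2.5, two-sided alpha 0.05 and a two-sample t-test. It gives no placebo mean. It adds that all active participants (12) will also be compared with all placebo participants (6).

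Protocol 3.1 says "the study is designed to observe a 30% reduction in the number of voids following gene transfer" and supports this with one row of PASS output. Its columns are power, N1, N2, ratio, alpha, beta, the two means and the two SDs: "0.80251 9 10 1.111 0.05000 0.19749 10.0 6.6 2.5 2.5". Protocol 10.3 repeats the table under the statement "The protocol is designed to observe a 30% reduction in the number of voids compared to placebo" and adds: "The sample size has been estimated assuming a standard deviation of 2.5 and a two sample t-test to have 80% power". SAP 5 has the same row and the same 30% wording.

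The design has two dose levels, each with 6 active and 3 placebo participants, and at most 18 in total. SAP 3.2 pools placebo (6) and compares it with each dose (6 each) and with both doses combined (12). It also plans a comparison between the two doses.

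**The concern.** The synopsis and the table cannot both be the basis for 80% power. One gives 6 per arm and a 30% reduction. The other gives 9 vs 10 and means that differ by 34%, yet is introduced as the calculation for 30%. The table also needs 19 patients, one more than the trial's maximum.

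The figure concerns voids per day, which SAP 9.1 treats as its primary efficacy result and tests with p-values. If a reader believes the trial had 80% power, a null result looks like evidence against a 30% effect. If power is below one half, the trial would miss such an effect more often than it found it. Protocol 2.1 says that safety and efficacy results may lead to an amendment adding doses, so a misread null result could affect that decision.

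**Working it through.** **Inputs.** SD 2.5, two-sided alpha 0.05 and a two-sample t-test come from the synopsis. The means 10.0 and 6.6 come from the PASS row. The comparisons 6 vs 6 and 12 vs 6 come from the synopsis and SAP 3.2. The synopsis gives no placebo mean, so 10.0 is taken from the PASS row as an assumption.

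**Effect sizes.** A 30% reduction is 0.30 × 10.0 = 3.0 voids per day. The PASS row has 10.0 − 6.6 = 3.4, and 3.4 / 10.0 = 34%.

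**Formula.** SE = 2.5 × √(1/n1 + 1/n2); noncentrality λ = difference / SE; df = n1 + n2 − 2. Power is the probability that a noncentral t variable with df and λ lies beyond ± the 97.5% point of t.

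**The plan's own row first.** For 9 vs 10 and difference 3.4: SE = 2.5 × √(1/9 + 1/10) = 1.149, λ = 2.960, df = 17, critical value 2.110. Power is 79.7% against the tabulated 80.25%, so the row reproduces closely for the design it describes.

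**The planned comparisons.**

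| Comparison | SE | df | Power, difference 3.0 (30%) | Power, difference 3.4 (34%) |
|---|---|---|---|---|
| 9 vs 10 (table only) | 1.149 | 17 | 69.2% | 79.7% |
| 6 vs 6 | 1.443 | 10 | **46.8%** | 56.6% |
| 12 vs 6 | 1.250 | 16 | **61.6%** | 72.4% |

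For 6 vs 6 and 3.0: λ = 3.0 / 1.443 = 2.078, below the critical value of 2.228, which is why power is under one half. For 12 vs 6: λ = 3.0 / 1.250 = 2.400 against 2.120.

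**Does another test give 80% with 6 per arm?** None of those tried does.

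| Test, 6 per arm | Difference 3.0 | Difference 3.4 |
|---|---|---|
| Two-sided z | 54.7% | 65.4% |
| One-sided t | 61.4% | 70.8% |
| One-sided z | 66.8% | 76.1% |
| Paired t, n = 6 | 65.5% | 75.9% |

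**Does another placebo mean give 80%?** With SD fixed at 2.5 and a 30% reduction:

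| Placebo mean (voids/day) | 6 vs 6 | 12 vs 6 |
|---|---|---|
| 8 | 32.5% | 43.8% |
| 10 | 46.8% | 61.6% |
| 12 | 61.5% | 77.2% |
| 14 | 74.6% | 88.3% |
| 15 | 80.2% | 92.2% |

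The 6 vs 6 comparison reaches 80% only at about 15 voids per day, and 12 vs 6 at about 12.4. The documents state neither mean. Alternatively, at a mean of 10.0, 6 vs 6 would need an SD of about 1.67 instead of 2.5.

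**What the design can detect.** The difference with 80% power is 4.49 voids per day for 6 vs 6 (45% of 10.0) and 3.73 for 12 vs 6 (37%). For a difference of 3.0, 80% power needs 12 per arm (80.2%; 11 per arm gives 76.3%). For 3.4 it needs 10 per arm (82.0%).

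**The case against.** The strongest reply is that this is a phase 1 safety trial. The protocol and SAP say its size was set on safety grounds, voids per day is a secondary outcome in the protocol, and SAP 7.3 calls the efficacy work exploratory, with unadjusted p-values. All of that is true, and it is why no extra patients are asked for. But the disclaimer covers only the primary (safety) endpoint. Protocol 3.1 and SAP 5 go straight on to the claim about voids, and Protocol 10.3 says the size was estimated to give 80% power.

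Second, the placebo mean of 10.0 is borrowed, because the synopsis sentence neither states a mean nor cites the table. That stands: the link between sentence and table is inferred from the shared power, SD, alpha and test, and 47% should be read with the range above. Inclusion sets no upper limit on frequency. Still, a mean of about 15 is needed to rescue the claim, and nothing in the documents supports it.

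Third, SAP 9.1 plans a linear mixed model over visits, not a t-test at one visit, and the documents do not say whether SD 2.5 is for counts or for change from baseline. This limits what 47% and 62% describe: a two-sample t-test at one visit. It does not defend the sentence, which names the t-test, and no within-patient correlation is given from which to compute a gain. Estimating the error from all three groups of six (15 df) raises 6 vs 6 only to 49.4%.

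Fourth, the plan has no futility or efficacy go/no-go rule, and SAP 9.1 reports 95% confidence intervals that would show the imprecision. That reduces the practical harm but does not make the stated figure right.

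**Conclusion.** The concern holds. On the synopsis's own SD, alpha and test, with the only mean in the documents, 6 per arm has 46.8% power for a 30% reduction, 33 percentage points below the stated 80%. The pooled comparison has 61.6%. The table cited in three places is nearly right for 9 vs 10 patients and a 34% reduction, but it describes neither the trial's comparisons nor the effect in the accompanying text.

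The exact percentages depend on a placebo mean of 10.0 voids per day, SD 2.5 and a t-test at a single visit. The mismatch between the synopsis (6 per arm, 30%) and the table (9 vs 10, 34%) depends on none of these. The error affects how the efficacy results will be read; it does not touch the safety objective or dose escalation.

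**What to change.** Delete the power sentence from the synopsis. Replace the 9 vs 10 table, and the 30% statement that introduces it, in Protocol 3.1, Protocol 10.3 and SAP 5. Use the same text in all places, for example:

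> The sample size is based on safety. For orientation, assuming a placebo mean of 10 voids per day, SD 2.5 and a two-sided two-sample t-test at the 0.05 level at one visit, power for a 30% reduction (10 to 7) is 47% for one dose vs pooled placebo (6 vs 6) and 62% for pooled active vs pooled placebo (12 vs 6). The differences detectable with 80% power are 4.5 and 3.7 voids per day. A non-significant result does not exclude a 30% reduction.

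State also whether SD 2.5 refers to the count at a visit or to change from baseline. If a different placebo mean was intended, give it with its basis and recompute.

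The cost is wording in the synopsis, two protocol sections and one SAP section. Patients, visits and analyses are unchanged. The stated power becomes less favourable.
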